8.1. Efficacy Assessments

8.1.1. Therapeutic Response Evaluation

Therapeutic response (success/failure) is a measure of the overall efficacy response. A therapeutic success refers to participants who have been deemed both a “microbiological success” (see Section 8.1.2.1) and a “clinical success” (see Section 8.1.3.1). All other combinations (other than clinical success + microbiological success) will be deemed failures for therapeutic response.

Therapeutic response will be determined by statistical programming for the TOC and Follow-up Visits.

Therapeutic response at TOC is the primary efficacy endpoint.

8.1.2. Bacteriology Samples

At the Baseline Visit, a pretreatment, clean-catch midstream urine sample must be obtained from all randomized participants for Gram stain, quantitative bacteriological culture, and in vitro antimicrobial susceptibility testing at a designated central

laboratory(ies). For inclusion in the micro-ITT Population, a baseline qualifying bacterial uropathogen is required as defined in [Appendix 4](#); for inclusion in the micro-ITT NTF-S Population, the baseline qualifying uropathogen must also be susceptible to nitrofurantoin. At the On-therapy, TOC, and Follow-up Visits, a clean-catch midstream urine sample will be obtained and sent to a designated central laboratory(ies) for Gram stain, quantitative bacteriological culture, and in vitro antimicrobial susceptibility testing. Identification and susceptibility testing of isolates recovered from urine specimens at all visits will also be conducted at a designated central laboratory(ies). Additional tests, as needed, to further characterize recovered isolates will also be performed by a designated central laboratory(ies). Instructions for sample collection, processing, and shipment are provided in the SRM and the laboratory manual. The study site should follow the Microbiology Procedures section of the laboratory manual to minimize potential contamination of the specimens.

8.1.2.1. Microbiological Outcome and Response

Only those participants who have a qualifying bacterial uropathogen (defined in [Appendix 4](#)) identified at Baseline will be evaluated for microbiological outcome and response by baseline qualifying uropathogen for the primary efficacy endpoint. The microbiological outcome and response to study treatment will be determined programatically for each participant/uropathogen prior to breaking of the study blind.

The microbiological outcome by baseline qualifying uropathogen is determined by comparing the baseline culture results to the culture results at each subsequent visit (see [Table 2](#), [Table 3](#), and [Table 4](#) for baseline qualifying uropathogen outcomes). The corresponding microbiological response (success or failure) “by uropathogen” is then assigned, as shown in [Table 3](#) and [Table 4](#). Participant-level microbiological response is a measure of the combined “by uropathogen” response(s). Participant-level microbiological success refers to participants who have been deemed a “microbiological success” for all of their “by uropathogen” microbiological responses. All other combinations (other than all “microbiological successes”) are deemed failures for participant-level microbiological response. The participant-level microbiological outcome and response definitions are provided in [Table 5](#).

Microbiological outcome criteria for new qualifying uropathogens (i.e., uropathogens not identified at Baseline) are defined by visit in

[Table 6](#), [Table 7](#), and [Table 8](#).

Table 2 Microbiological Outcome by Baseline Qualifying Uropathogen at the On-Therapy Visit

Defining Criteria	Outcome
A quantitative urine culture taken at the On-therapy Visit shows that the qualifying bacterial uropathogen recovered at Baseline is reduced to $<10^3$ CFU/mL, without the participant receiving other systemic antimicrobials before the On-therapy Visit	Microbiological eradication
A quantitative urine culture taken at the On-therapy Visit shows that the qualifying bacterial uropathogen recovered at Baseline grows $\geq 10^3$ CFU/mL, without the participant receiving other systemic antimicrobials before the On-therapy Visit	Microbiological persistence
1) The On-therapy urine culture result is missing, or 2) The participant received other systemic antimicrobials before the On-therapy Visit	Unable to determine

CFU=colony-forming units.

Table 3 Microbiological Outcome and Response by Baseline Qualifying Uropathogen at the Test-of-Cure Visit

Defining Criteria	Outcome	Response
Participants considered microbiological failures at the TOC Visit will also be considered microbiological failures at the Follow-up Visit.		
A quantitative urine culture taken at the TOC Visit shows reduction of the qualifying bacterial uropathogen recovered at Baseline to $<10^3$ CFU/mL, without the participant receiving other systemic antimicrobials before the TOC Visit	Microbiological eradication	Microbiological success
A quantitative urine culture taken at the TOC Visit shows that the qualifying bacterial uropathogen recovered at Baseline, and which was also shown to persist or unable to determine at the On-therapy Visit, grows $\geq 10^3$ CFU/mL, without the participant receiving other systemic antimicrobials before the TOC Visit	Microbiological persistence	Microbiological failure
A quantitative urine culture taken at the TOC Visit shows that the qualifying bacterial uropathogen recovered at Baseline, and which was also shown to be eradicated at the On-therapy Visit, grows $\geq 10^3$ CFU/mL, without the participant receiving other systemic antimicrobials before the TOC Visit	Microbiological recurrence	Microbiological failure
1) The TOC urine culture result is missing, or 2) The participant received other systemic antimicrobials before the TOC Visit	Unable to determine	Microbiological failure

CFU=colony-forming units; TOC=Test-of-Cure.

Table 4 Microbiological Outcome and Response by Baseline Qualifying Uropathogen at the Follow-Up Visit

Defining Criteria	Outcome	Response
Participants considered microbiological failures at the TOC Visit will also be considered microbiological failures at the Follow-up Visit.		
A quantitative urine culture taken at the Follow-up Visit shows reduction of the qualifying bacterial uropathogen recovered at Baseline to 10^3 CFU/mL, following microbiological eradication at the TOC Visit, without the participant receiving other systemic antimicrobials before the Follow-up Visit	Sustained microbiological eradication	Microbiological success
A quantitative urine culture taken at the Follow-up Visit shows that the qualifying bacterial uropathogen recovered at Baseline grows $\geq 10^3$ CFU/mL, following microbiological eradication at the TOC Visit, without the participant receiving other systemic antimicrobials before the Follow-up Visit	Microbiological recurrence	Microbiological failure
A quantitative urine culture taken at the Follow-up Visit shows that the qualifying bacterial uropathogen recovered at Baseline grows $\geq 10^3$ CFU/mL, and also did not achieve an outcome of microbiological eradication at the TOC Visit, without the participant receiving other systemic antimicrobials before the Follow-up Visit	Microbiological persistence	Microbiological failure
A quantitative urine culture taken at the Follow-up Visit shows reduction of the qualifying bacterial uropathogen recovered at Baseline to 10^3 CFU/mL, and also did not achieve an outcome of microbiological eradication at the TOC Visit, without the participant receiving other systemic antimicrobials before the Follow-up Visit	Delayed microbiological eradication	Microbiological failure
1) The Follow-up urine culture result is missing, or 2) The participant received other systemic antimicrobials before the Follow-up Visit	Unable to determine	Microbiological failure

CFU=colony-forming units; TOC=Test-of-Cure.

Table 5 Participant-Level Microbiological Outcome and Response Definitions per Study Visit

Defining Criteria at the On-Therapy Visit	Outcome	Response
All qualifying baseline uropathogens have a microbiological outcome of eradication at On-therapy	Microbiological eradication	NA
At least one qualifying baseline uropathogen has an outcome of persistence at On-therapy	Microbiological persistence	NA
All qualifying baseline uropathogen outcomes are unable to determine at On-therapy	Unable to determine	NA
Defining Criteria at the TOC Visit		
All qualifying baseline uropathogens have a microbiological outcome of eradication at TOC	Microbiological eradication	Microbiological success
At least one qualifying baseline uropathogen has an outcome of persistence at TOC	Microbiological persistence	Microbiological failure
At least one qualifying baseline uropathogen has an outcome of recurrence and none have an outcome of persistence at TOC	Microbiological recurrence	Microbiological failure
All qualifying baseline uropathogen outcomes are unable to determine at TOC	Unable to determine	Microbiological failure
Defining Criteria at the Follow-up Visit		
All qualifying baseline uropathogens have a microbiological outcome of sustained eradication at Follow-up	Sustained microbiological eradication	Microbiological success
At least one qualifying baseline uropathogen has an outcome of recurrence and none have an outcome of persistence at Follow-up	Microbiological recurrence	Microbiological failure
At least one qualifying baseline uropathogen has an outcome of persistence at Follow-up	Microbiological persistence	Microbiological failure
At least one qualifying baseline uropathogen has an outcome of delayed eradication and none have an outcome of persistence or recurrence at Follow-up	Delayed microbiological eradication	Microbiological failure
All qualifying baseline uropathogen outcomes are unable to determine at Follow-up	Unable to determine	Microbiological failure

NA=Not applicable; TOC=Test-of-Cure.

Table 6 Microbiological Outcome by New Qualifying Uropathogen at the On-Therapy Visit

Defining Criteria	Outcome
A new qualifying bacterial uropathogen, not identified at Baseline, is documented by quantitative urine culture at the On-therapy Visit	New uropathogen

Table 7 Microbiological Outcome by New Qualifying Uropathogen at the Test-of-Cure Visit

Defining Criteria	Outcome
A new qualifying bacterial uropathogen, not identified at Baseline, is documented by quantitative urine culture at the Test-of-Cure Visit in a participant who did not achieve a clinical outcome of clinical resolution at the Test-of-Cure Visit	New infection
A new qualifying bacterial uropathogen, not identified at Baseline, is documented by quantitative urine culture at the Test-of-Cure Visit in a participant who did achieve a clinical outcome of clinical resolution at the Test-of-Cure Visit	Colonization

Table 8 Microbiological Outcome by New Qualifying Uropathogen at the Follow-up Visit

Defining Criteria	Outcome
A new qualifying bacterial uropathogen, not identified at Baseline, is documented by quantitative urine culture at the Follow-up Visit in a participant who did not achieve a clinical resolution at the Follow-up Visit	New infection
A new qualifying bacterial uropathogen, not identified at Baseline, is documented by quantitative urine culture at the Follow-up Visit in a participant who did achieve a clinical resolution at the Follow-up Visit	Colonization

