- a. A study physician or otherwise appropriately medically trained staff will determine the individual clinical signs and symptoms scores for acute cystitis (Appendix 6), which will then be used to programmatically determine the clinical outcome. The same scorer will be used at all assessment time points for each participant, on all occasions, whenever possible.

Table 10 Clinical Outcome and Response at the Test-of-Cure Visit

Defining Criteria	Outcome^a	Response
Resolution of signs and symptoms of acute cystitis present at Baseline (and no new signs or symptoms), without the participant receiving other systemic antimicrobials before the TOC Visit	Clinical resolution	Clinical success
Improvement in total symptom scores from Baseline, but not complete resolution, without the participant receiving other systemic antimicrobials before the TOC Visit	Clinical improvement	Clinical failure
Worsening or no change in total symptom scores from Baseline or the participant received other systemic antimicrobials for the current infection before or on the date of the TOC Visit	Clinical worsening	Clinical failure
1) The Baseline score is missing, or 2) The TOC assessment is missing, or 3) The participant received other systemic antimicrobials not for the current infection prior to the assessment (unless clinical worsening criteria were met)	Unable to determine	Clinical failure

TOC = Test-of-Cure

- a. A study physician or otherwise appropriately medically trained staff will determine the individual clinical signs and symptoms scores for acute cystitis ([Appendix 6](#)), which will then be used to programmatically determine the clinical outcome. The same scorer will be used at all assessment time points for each participant, on all occasions, whenever possible.

Table 11 Clinical Outcome and Response at the Follow-up Visit

Defining Criteria	Outcome^a	Response
Resolution of signs and symptoms of acute cystitis demonstrated at the TOC Visit persist at the Follow-up Visit (and no new signs and symptoms), without the participant receiving other systemic antimicrobials before the Follow-up Visit	Sustained clinical resolution	Clinical success
Resolution of signs and symptoms of acute cystitis present at Baseline (and no new signs or symptoms), after clinical failure at TOC, without the participant receiving other systemic antimicrobials before the Follow-up Visit	Delayed clinical resolution	Clinical failure

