20	Intent-to-treat	EFF_L3	Listing of Susceptibility Results	Non-ICH Listing	AAC	AAC
21	Micro-ITT	EFF_L4	Listing of Clinical Response, Microbiological Outcome and Response, Therapeutic Response, Study Drug MIC and Zone Diameter Results by Qualifying Baseline Uropathogen	Non-ICH Listing	AAC	AAC

Listings						
No.	Population	IDSL / Example Shell	Title	Programming Notes	Deliverable	
					If study stops	If study continues
22	Intent-to-Treat	EFF_L4	Listing of Clinical Response, Microbiological Outcome and Response, Therapeutic Response, MIC and Zone Diameter Results for Uropathogens with a 4-fold Increase in Study Treatment MIC	Non-ICH Listing	AAC	AAC
CCI						
24	Intent-to-treat		Listing of Genetic Characterization Results	Non-ICH Listing	AAC	AAC
25	Intent-to-treat		Listing of New Qualifying Uropathogens	Non-ICH Listing	AAC	AAC
26	Micro-ITT		Listing of Sequence Typing and Phenotypic Subcategories for Qualifying Uropathogens from Microbiological Failures	Non-ICH Listing	AAC	AAC
Adverse Events						
27	Safety	AE2	Listing of Relationship Between System Organ Class and Verbatim Text	Non-ICH Listing	AAC	AAC
28	Safety	AE7	Listing of Subject Numbers for Individual Adverse Events	ICH Listing	AAC	AAC
29	Safety	AE8CP	Listing of All Adverse Events	ICH Listing	AAC	AAC
Serious and Other Significant Adverse Events						
30	Safety	AE8CP	Listing of Study Drug Related Adverse Events	ICH Listing	AAC	AAC
31	Safety	SAFE_L2	Listing of Serious Adverse Events (Fatal & Non-Fatal)	ICH Listing	HDL	HDL
31.1	Safety		Listing of Fatal Serious Adverse Events	ICH Listing	AAC	AAC
32	Safety	AE8CP	Listing of Adverse Events Leading to Discontinuation of Study Treatment or Withdrawal from Study	ICH Listing	AAC	AAC

Listings						
No.	Population	IDSL / Example Shell	Title	Programming Notes	Deliverable	
					If study stops	If study continues
33	Safety	AE8CP	Listing of Cardiovascular and Gastrointestinal Adverse Events of Special Interest	ICH Listing	AAC	AAC
34	Safety	AE8CP	Listing of Acetylcholinesterase-Inhibition Adverse Events of Special Interest	ICH Listing	AAC	AAC
35	Safety	AE8CP	Listing of Non-Gastrointestinal Acetylcholinesterase-Inhibition Adverse Events of Special Interest	ICH Listing	AAC	AAC
All Laboratory						
36	Safety	LB5A	Listing of Clinical Chemistry Toxicities of Grade 3 or Higher	ICH Listing	AAC	AAC
37	Safety	LB5A	Listing of All Clinical Chemistry Data for Subjects with Toxicities of Grade 3 or Higher	ICH Listing	AAC	AAC

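### Protocol Tables 7 and 8 call a new qualifying uropathogen a new infection whenever clinical resolution is not assigned, even if the symptom score is zero or missing

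*Protocol*

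**What the plan says.** Protocol Section 8.1.2.1 defines outcomes for qualifying uropathogens that were absent at Baseline. Table 7 starts from the finding that "A new qualifying bacterial uropathogen, not identified at Baseline, is documented by quantitative urine culture at the Test-of-Cure Visit" and offers two labels. It is *New infection* "in a participant who did not achieve a clinical outcome of clinical resolution at the Test-of-Cure Visit" and *Colonization* "in a participant who did achieve a clinical outcome of clinical resolution at the Test-of-Cure Visit". Table 8 repeats the split at Follow-up, with *New infection* assigned "in a participant who did not achieve a clinical resolution at the Follow-up Visit". Neither table has a third category.

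Clinical resolution is defined in Section 8.1.3.1. At TOC, Table 10 requires that baseline symptoms have resolved "and no new signs or symptoms), without the participant receiving other systemic antimicrobials before the TOC Visit". A participant is *Clinical worsening* if her score is unchanged or worse, "or the participant received other systemic antimicrobials for the current infection before or on the date of the TOC Visit". She is *Unable to determine* if the baseline score or TOC assessment is missing, or if she took other systemic antimicrobials for a different infection before the assessment. Table 11 has matching rows at Follow-up, but its two resolution outcomes are *Sustained* and *Delayed* clinical resolution.

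For organisms present at Baseline, Tables 2 to 4 carry an antimicrobial condition (in Table 2, "without the participant receiving other systemic antimicrobials before the On-therapy Visit") and an *Unable to determine* row. In the unredacted SAP, the display found for new organisms is the "Listing of New Qualifying Uropathogens" in Section 11.9.11.

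**The concern.** The difference between infection and colonization should turn on whether the new organism comes with symptoms. Tables 7 and 8 decide it by an efficacy outcome built for another purpose. In the primary estimand, use of other systemic antimicrobials counts as failure because it confounds the assessment of efficacy. That is reasonable for a success rate, but it says nothing about whether a woman had symptoms when the new organism was grown.

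The label *New infection* therefore mixes three groups: women with symptoms, women with an observed score of zero who lost the resolution outcome for another reason, and women whose symptoms at the visit are unknown. An outcome that the protocol itself calls indeterminate becomes a definite infection. At stake is the meaning of an exploratory count, not the trial's main conclusion.

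**Working it through.** The plan states no figure to reproduce, so the check follows the rules through each possible case.

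**Inputs.** Protocol Tables 10 and 7 for TOC, Tables 11 and 8 for Follow-up, and SAP Section 7.1.1.3, under which one missing symptom item makes the total score missing.

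**TOC, for a participant with a new qualifying uropathogen:**

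| Baseline score | TOC score | Other systemic antimicrobial | Table 10 outcome | Table 7 label |
|---|---|---|---|---|
| present | 0 | none | Clinical resolution | Colonization |
| present | 0 | current infection | Clinical worsening | New infection |
| present | 0 | another infection | Unable to determine | New infection |
| missing | 0 | none, or another infection | Unable to determine | New infection |
| missing | 0 | current infection | Clinical worsening | New infection |
| either | missing | none, or another infection | Unable to determine | New infection |
| either | missing | current infection | Clinical worsening | New infection |
| either | above 0 | any | never resolution | New infection |

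**Count.** Take baseline score (present, missing) × TOC score (0, improved, same or worse, missing) × antimicrobial (none, current infection, another infection): 2 × 4 × 3 = 24 combinations.

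- Score 0: 2 × 3 = 6 combinations. One gives *Colonization*. Five give *New infection*: two with the baseline score present and three with it missing.
- Score missing: 2 × 3 = 6 combinations, all *New infection*, with no symptom information.
- Score above 0: 2 × 2 × 3 = 12 combinations, all *New infection*, as intended.
- Total: 1 + 5 + 6 + 12 = 24.

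These are counts of logical cases, not expected proportions of participants. They do not depend on whether *Clinical worsening* or *Unable to determine* takes precedence, since neither is clinical resolution.

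**Follow-up.** Take a woman given rescue at TOC, after the TOC procedures, who has a score of zero and a new qualifying uropathogen at Day 28. Table 11 makes her *Clinical worsening*, because she took an antimicrobial for the current infection before the visit. Table 8 then makes her a *New infection*.

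Table 8 is also less exact than Table 7: it speaks of a clinical resolution without naming a Table 11 outcome. If only *Sustained* counts, a woman who failed clinically at TOC, took no other antimicrobial and scores zero at Follow-up (*Delayed*) is also a *New infection*. If *Delayed* counts too, she is *Colonization*. The protocol does not say which.

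**The case against.** The strongest reply is that reusing the programmed clinical outcome follows the protocol's composite strategy, and that the label is descriptive, with no success or failure attached. That is a fair account of how the rule arose. It does not explain why an observed score of zero, or an outcome declared indeterminate, should become a definite infection.

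Several limits stand:

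- **Timing of rescue.** Protocol Sections 4.1 and 8 ask that all TOC procedures be completed before another antibiotic is started. Where this is followed, culture and score at TOC precede rescue. It does not cover drugs given elsewhere or for another infection, nor the Follow-up Visit.
- **Missing baseline scores.** These should be rare, because entry requires at least two symptoms and Section 8.1.3.1 requires a baseline score of at least 2.
- **Exploratory status.** The amendment history (Appendix 15, Amendment 1) moved this outcome from secondary to exploratory. The exploratory analysis text is redacted in both documents, and SAP Section 5.5 treats every efficacy endpoint other than the primary as descriptive.

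A reader might infer more than the text supports:

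- *Missed visits inflate new infections.* They do not. Both tables require a culture at the visit, so a wholly missed visit contributes none. Only a culture with a missing score can.
- *Every woman without a score is colonized.* If the visit score is missing, her symptoms are unknown. The label is unsupported, not shown to be wrong.
- *The new organism is attributed to the randomised drug.* Tables 6 to 8 make no causal attribution.
- *The comparison between arms is biased.* Rescue and missing scores could differ by arm, but no between-arm analysis of this outcome is visible, so this cannot be established.

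**Conclusion.** The concern holds as a defect in a stated rule. Tables 7 and 8 give the label *New infection* to some women with an observed symptom score of zero, and to women with a culture but no visit score. The clearest case is Follow-up after rescue at TOC.

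Its importance is small. It touches one exploratory, descriptive outcome. It does not enter therapeutic response, the noninferiority test or the sample size. Its size cannot be stated: the documents give no rates of new uropathogens, of rescue with symptom resolution, or of cultures without scores, so any percentage would rest on invented inputs.

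The conclusion assumes that Table 8 is read through the Table 11 outcomes, as Table 7 is explicitly read through Table 10. It also rests on the protocol text alone. The redacted SAP section may contain a different rule, which can be neither confirmed nor excluded.

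**What to change.** In Tables 7 and 8:

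1. Base the split on the observed total symptom score at that visit: above zero is *New infection*, zero is *Colonization*.
2. Add *Unable to determine* for a missing visit score.
3. Flag, or tabulate separately, new uropathogens found after other systemic antimicrobials, without letting that use alone set the label. Moving all such women to the indeterminate row would discard those who have symptoms and a new uropathogen after rescue.
4. Use the same rule in the SAP derivation, if it does not do so already.

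Applied to the 24 TOC combinations, this gives 6 *Colonization*, 12 *New infection* and 6 *Unable to determine*. It also removes the doubt about *Sustained* and *Delayed* resolution in Table 8, because the split no longer uses those outcomes.

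No new data are needed. The Schedule of Activities already collects scores and cultures at each visit, and Protocol Section 6.5 requires dates and reason for use of concomitant medication. The cost is a few table rows and a short programming change. The downside is slightly fewer new infections and one extra category to report.
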